#### 5.0 ELIGIBILITY CRITERIA

# 5.1 Inclusion Criteria

- 5.1.1. Age ≥ 18 years of age.
- 5.1.2. Presence of SARS-CoV2 infection, confirmed by real-time reverse transcription polymerase chain reaction (RT-PCR) assay from a nasopharyngeal swab specimen or other diagnostic test for SARS-CoV2.
- 5.1.3. Serum D-Dimer ≥ 2X ULN.
- 5.1.4. Patients with Acute Respiratory Distress Syndrome (ARDS) as determined by the following criteria (Berlin criteria adaptation):
  - a. Radiographic evidence of bilateral lung disease (opacities or ground glass opacification) on chest radiograph (CXR) or computed tomography (CT), and the opacities not fully explained by pleural effusions, cardiac failure or fluid overload.
  - b. Impairment of oxygenation, defined by either a) the ratio of arterial oxygen tension to fraction of inspired oxygen (PaO2/FiO2) ≤ 300 mmHg, or b) the use of supplemental oxygen to support an SpO2 ≥ 90%.
- 5.1.5. Patients must provide voluntary written informed consent to be eligible for study. For patients who are medically unable to provide consent, their designated proxy or legal guardian will provide informed consent. The consenting process is described in Appendix II.
- 5.1.6. Patients actively participating in another clinical trial for the management of SARS-CoV2 are eligible provided those trials do not directly involve an anti-platelet, anti-coagulant or anti-fibrinolytic agent. (Patients enrolled on investigational trials utilizing anti-viral specific agents, cytokine inhibitors, tyrosine kinase inhibitors, or other anti-inflammatory agents are still eligible).

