# 1.0 STUDY SYNOPSIS

This is an investigator initiated, open label trial of defibrotide for therapy of patients with SARS-CoV2 related acute respiratory distress syndrome (ARDS). The primary endpoint is safety and tolerability. Secondary endpoints will assess response and ventilator free survival.

*Eligibility*: Patients ≥ 18 years in age with evidence of SARS-CoV2 related ARDS. All patients must exhibit signs of coagulopathy evidenced by a D-dimer > 2X ULN.

**Study therapy:** Defibrotide will be administered intravenously (IV) every 6 hours (Q6H) for 7 days of therapy. Patients who meet defined toxicity and/or efficacy criteria within the 7-day period may cease study therapy at that earlier time point. Patients with a partial response to study therapy by day 7 (defined as > 20% decrease in supplemental oxygen) may continue to receive an additional 7 days of therapy (14 days total therapy). Toxicity (including rate of hemorrhage / bleeding) will be assessed. Each patient will be monitored for 14 days, including 7 days of therapy and 7 days of post-therapy observation.

**Sample Size:** 12 patients. An interim assessment for toxicity and early mortality will be performed after the first six patients have enrolled. Accrual may proceed to a maximum of 12 patients, if the stopping rules are not met within the first six patients.

**Other:** The study will target patients with either early or late-phase ARDS, provided patients have not required mechanical ventilation for > 7 consecutive days. The study allows co-enrollment with other SARS-CoV2 therapy trials, provided those trials are not also utilizing other anti-coagulant or fibrinolytic agents.

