#### 5.2 Exclusion Criteria

- 5.2.1. Thrombolytic treatment and/or anticoagulant treatment at the use of non-therapeutic-doses within 12 hours of study entry. [Note: the use of non-therapeutic doses of heparin (≤7,500 units Q8Hours) or low molecular weight heparin (≤ 1 mg/kg/day) is allowed}. In addition, the administration of heparin flushes for centrally placed catheters, fibrinolytic instillation for central venous line occlusion, or in the in-flow circuit for patients on continuous veno-venous hemodialysis is allowed].
- 5.2.2. Clinically significant acute bleeding, including (but not limited to one of the following): pulmonary hemorrhage (diffuse alveolar hemorrhage), intracranial bleed, gastro-intestinal hemorrhage (gross hematemesis or

- hematochezia), gross hematuria or uncontrolled epistaxis irrespective of the amount of blood loss, within the prior 3 days.
- 5.2.3. On mechanical ventilation for > 7 consecutive days (> 168 hours).
- 5.2.4. Serum platelet count < 50,000/uL. Transfusion of platelets to achieve a level > 50,000/uL is not allowed for eligibility.
- 5.2.5. Serum fibrinogen < 150 mg/dl. Transfusion of fresh frozen plasma or cryoprecipitate to achieve a level > 150 mg/dl is not allowed for eligibility.
- 5.2.6. The presence of an uncontrolled systemic infection (other than COVID-19).
- 5.2.7. Hemodynamic instability as defined by a requirement for 2 or more vasopressors (not including renal-doses of dopamine).
- 5.2.8. Concurrent use of Extracorporeal membrane oxygenation (ECMO).
- 5.2.9. Patients with a previously known hypersensitivity reaction to defibrotide, or any of its excipients.
- 5.2.10. Females who are pregnant or breastfeeding.
- 5.2.11. History of cerebrovascular accident (i.e. thrombotic or hemorrhagic stroke) within 3 months prior to study entry.

**Other considerations:** There is no exclusion for hepatic or renal failure at the time of study entry, including the use of hemodialysis or peritoneal dialysis.

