# 6.6 Concurrent Medications

Patients may NOT be treated concurrently with therapeutic dosing of antifibrinolytics, or anticoagulants, including (but not limited to) therapeutic dosing with heparin, systemic t-PA, or warfarin. The use of non-therapeutic doses of heparin ( $\leq 7,500$  units Q8Hours) or low molecular weight heparin ( $\leq 1$  mg/kg/day) is allowed. Patients may also receive heparin or other anticoagulants for routine central venous line management, intermittent dialysis or ultrafiltration. Fibrinolytic instillation for central venous line occlusion is also permitted.

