# 9.0 OFF STUDY CRITERIA

Defibrotide will be discontinued for any of the following reasons:

- Withdrawal of consent / patient choice.
- The patient experiences an adverse event which, in the opinion of the Investigator, contraindicates continuation in the study.
- Protocol violation, including disallowed concomitant therapy.
- The Investigator considers it not in the patient's best interest to continue.
- Defibrotide-related toxicity (including hemorrhage as defined in section 6.4)
- Subject death.

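### Criterion 5.1.6 bars co-enrolment in trials of anti-fibrinolytic agents where the synopsis bars fibrinolytic agents, the opposite class, and section 6.6 repeats the slip

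*Combined protocol and SAP*

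**What the plan says.** Two places in the combined protocol and SAP govern co-enrolment.

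- Section 1.0 (Study Synopsis, *Other*) allows it "provided those trials are not also utilizing other anti-coagulant or fibrinolytic agents".
- Section 5.1.6 (Inclusion Criteria) allows it "provided those trials do not directly involve an anti-platelet, anti-coagulant or anti-fibrinolytic agent". It then lists trial types that remain acceptable: antivirals, cytokine inhibitors, tyrosine kinase inhibitors and other anti-inflammatory agents.

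Two further places govern the drugs themselves.

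- Section 5.2.1 (Exclusion Criteria) excludes "Thrombolytic treatment and/or anticoagulant treatment" in the 12 hours before study entry. Among its exceptions is "fibrinolytic instillation for central venous line occlusion".
- Section 6.6 (Concurrent Medications) states: "Patients may NOT be treated concurrently with therapeutic dosing of antifibrinolytics, or anticoagulants". Its non-exhaustive examples are "therapeutic dosing with heparin, systemic t-PA, or warfarin". It adds: "Fibrinolytic instillation for central venous line occlusion is also permitted".

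Section 9.0 (Off Study Criteria) lists, among the reasons for stopping defibrotide, "Protocol violation, including disallowed concomitant therapy".

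**The concern.** The synopsis and the operative eligibility criterion differ by a prefix that reverses the meaning. A screener working from section 5.1 would turn away a patient from an anti-fibrinolytic trial, which the synopsis does not mention. The same screener would find nothing in 5.1.6 to stop a patient from a fibrinolytic trial, which the synopsis forbids.

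The class matters because of the endpoint. Section 8.1 makes hemorrhagic complications within 14 days of starting treatment the primary outcome, and section 4.0 describes defibrotide itself as anti-coagulant and pro-fibrinolytic. A second clot-dissolving drug would add to the risk being measured. Under section 8.5 a patient is evaluable after one dose. The trial has one arm and at most 12 patients, so no comparator would help to attribute a bleed. Section 8.3 suspends accrual at three major bleeds among the first six patients, so one bleed in a co-treated patient would be one third of that early threshold.

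**Working it through.** The plan gives no figure on this point, so the check is a comparison of wording.

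**Step 1. Every mention of the class in a rule that bars or permits something.**

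| Section | Role of the rule | Class named |
|---|---|---|
| 1.0 Synopsis | bars other trials | fibrinolytic |
| 5.1.6 | bars other trials | anti-fibrinolytic |
| 5.2.1 | bars treatment before entry | thrombolytic |
| 5.2.1 | permits line instillation | fibrinolytic |
| 6.6 | bars treatment during therapy | antifibrinolytics |
| 6.6 | permits line instillation | fibrinolytic |

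Total: 1 + 1 + 2 + 2 = 6 mentions. Four say fibrinolytic or thrombolytic and two say the opposite. Among the four barring rules alone the split is 2 to 2, so the tally does not settle which class was meant. The t-PA example in 6.6 is not counted.

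**Step 2. Which class was meant.**

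- In 6.6 the examples under antifibrinolytics and anticoagulants are heparin, systemic t-PA and warfarin. Heparin and warfarin are anticoagulants. t-PA is a plasminogen activator, hence a fibrinolytic, and belongs to neither named class. The example fits only if the first class was meant to be fibrinolytics.
- Sections 5.2.1 and 6.6 both make an exception for fibrinolytic instillation into a blocked line. Such an exception is needed only where fibrinolytics are otherwise barred.
- Section 5.2.1 bars thrombolytic treatment outright.
- Section 4.0 calls defibrotide pro-fibrinolytic, so the additive bleeding risk comes from fibrinolytics.

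**Step 3. The two co-enrolment lists.**

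- Synopsis: anti-coagulant, fibrinolytic (2 classes).
- 5.1.6: anti-platelet, anti-coagulant, anti-fibrinolytic (3 classes).
- In common: anti-coagulant (1 class).

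**Step 4. What the other rules leave open if 5.1.6 and 6.6 are read literally.**

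- 5.2.1 looks back only 12 hours. It does not reach a patient in a fibrinolytic trial who was dosed earlier or has yet to be dosed.
- 6.6 names systemic t-PA. Another systemic fibrinolytic falls outside its literal class label, although the open-ended list would lead a sensible reader to include it.
- 9.0 acts only once disallowed therapy has been given. By then a patient who has had one dose of defibrotide already counts toward the primary endpoint.

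**The case against.** The strongest reply is that the word is wrong but hardly matters. The intended meaning is plain from context, and a patient actually receiving a systemic fibrinolytic would meet the synopsis, 5.2.1, the named t-PA in 6.6 and section 9.0. Fibrinolytic trials are also absent from the list in 5.1.6 of trials that remain acceptable. Nothing in the documents shows that a competing fibrinolytic trial was open to these patients at this single center. Most of this stands, and it is why the point is minor.

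Three narrower objections have some force. The count of four against two mixes bans with permissions, so the t-PA example is the better evidence of intent. The line-instillation exceptions qualify drug-treatment rules, so they bear on co-enrolment only by analogy. The anti-platelet difference is not a true conflict: the body of the protocol is simply stricter than its summary.

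It could also be said that barring anti-fibrinolytics was deliberate, since they would oppose defibrotide's stated action. That does not remove the problem. Section 5.1.6 would then omit fibrinolytics, which the synopsis bars, and t-PA would still be misplaced in 6.6.

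The safeguards narrow the gap but do not close it. The wrong term also sits in an eligibility rule and a prohibited-medication rule, not in background text.

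**Conclusion.** The concern holds. Sections 5.1.6 and 6.6 name the opposite of the drug class that the synopsis, 5.2.1 and the t-PA example show was intended. Applied as written, 5.1.6 admits a patient whom the synopsis excludes.

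The certainty lies in the text and not in any harm. The number of patients affected cannot be estimated from the documents and may be zero. The link to the primary endpoint is conditional on such a patient enrolling. This is a low-severity wording correction worth making because it concerns a bleeding-risk rule in a bleeding-safety trial. The conclusion assumes that the published wording is the sponsor's own. A text-extraction fault is unlikely, because the anti- form appears in two sections with different hyphenation.

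**What to change.** - In 5.1.6, replace *anti-fibrinolytic* with *fibrinolytic/thrombolytic*.
- In 6.6, replace *antifibrinolytics* with *fibrinolytics/thrombolytics*.
- Use one list of barred trial classes in both the synopsis and 5.1.6: anti-platelet, anti-coagulant, fibrinolytic/thrombolytic.
- If the sponsor also wants anti-fibrinolytics barred, name them as an additional class and not in place of fibrinolytics.

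The cost is a wording amendment. Compared with the literal text of 5.1.6 the co-enrolment pool becomes marginally narrower for fibrinolytic trials, which the synopsis already bars.

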#### 5.2 Exclusion Criteria

- 5.2.1. Thrombolytic treatment and/or anticoagulant treatment at the use of non-therapeutic-doses within 12 hours of study entry. [Note: the use of non-therapeutic doses of heparin (≤7,500 units Q8Hours) or low molecular weight heparin (≤ 1 mg/kg/day) is allowed}. In addition, the administration of heparin flushes for centrally placed catheters, fibrinolytic instillation for central venous line occlusion, or in the in-flow circuit for patients on continuous veno-venous hemodialysis is allowed].
- 5.2.2. Clinically significant acute bleeding, including (but not limited to one of the following): pulmonary hemorrhage (diffuse alveolar hemorrhage), intracranial bleed, gastro-intestinal hemorrhage (gross hematemesis or

- hematochezia), gross hematuria or uncontrolled epistaxis irrespective of the amount of blood loss, within the prior 3 days.
- 5.2.3. On mechanical ventilation for > 7 consecutive days (> 168 hours).
- 5.2.4. Serum platelet count < 50,000/uL. Transfusion of platelets to achieve a level > 50,000/uL is not allowed for eligibility.
- 5.2.5. Serum fibrinogen < 150 mg/dl. Transfusion of fresh frozen plasma or cryoprecipitate to achieve a level > 150 mg/dl is not allowed for eligibility.
- 5.2.6. The presence of an uncontrolled systemic infection (other than COVID-19).
- 5.2.7. Hemodynamic instability as defined by a requirement for 2 or more vasopressors (not including renal-doses of dopamine).
- 5.2.8. Concurrent use of Extracorporeal membrane oxygenation (ECMO).
- 5.2.9. Patients with a previously known hypersensitivity reaction to defibrotide, or any of its excipients.
- 5.2.10. Females who are pregnant or breastfeeding.
- 5.2.11. History of cerebrovascular accident (i.e. thrombotic or hemorrhagic stroke) within 3 months prior to study entry.

**Other considerations:** There is no exclusion for hepatic or renal failure at the time of study entry, including the use of hemodialysis or peritoneal dialysis.

#### 6.0 STUDY THERAPY

#### 6.1 General

The study is designed as a single-center, open label trial investigating the use of defibrotide for the treatment of SARS-CoV2 related ARDS. The investigational agent is supplied by Jazz Pharmaceuticals.

# 6.2 Defibrotide dosing and administration

All patients will receive 25 mg/kg/day of defibrotide, given in 4 divided doses (approximately Q6H), each dose infused intravenously (IV) over an approximate 2-hour period. No dose shall be infused within 3 hours of a prior dose. The defibrotide will be administered in 0.9% Sodium Chloride or 5% dextrose in water IV and mixed to a concentration of 4 - 20 mg/mL.

The dose of Defibrotide (6.25 mg/kg Q6H) will be based on the patient's recorded weight at the time of study entry. Each of the 4 divided doses per day will be rounded to the nearest 10 mg for adults (>35 kg) and the nearest 5 mg for children (<35 kg) in order to facilitate efficient drug administration. Total daily dose for all patients will be 25 mg/kg. No premedication is required with dosing. Vitals (Blood Pressure, Heart Rate, Respiratory Rate) should be obtained at the start and completion of the first infusion, and with subsequent infusions where clinically possible. There is no dosing adjustment for hepatic or renal dysfunction, including hemodialysis.

Administer the diluted defibrotide solution using an infusion set equipped with a 0.2 micron inline filter. Flush the intravenous administration line (peripheral or central) with 5% Dextrose Injection, USP or 0.9% Sodium Chloride Injection, USP immediately before and after administration. Do not co-administer defibrotide and other intravenous drugs concurrently within the same intravenous line.

Amendment 2.0

# 6.3 Therapy duration

The planned duration of study therapy is 7 days (168 hours) from study entry, with the following qualifications:

- a. Patients who respond to study therapy prior to the 7-day period, as evidenced by a decline in the WHO Ordinal Score by  $\geq$  2 points (APPENDIX 1) for > 48 consecutive hours, may discontinue study therapy at that earlier time point.
- b. Patients who have not responded to study therapy by day 7 of therapy, evidenced by <20% reduction (or a worsening) of the amount of supplemental oxygen they are receiving, will discontinue study therapy at that time point (day 7).
- c. Patients who have evidence of a partial pulmonary response by day 7 ( $\geq$ 20% reduction in supplemental O2 requirement, but still require supplemental oxygen) may elect to continue to receive study drug through an additional 7 days of study (total 14-day therapy course).

# 6.4 Criteria to Hold Study Therapy

Study drug will be held in the following settings:

Patients who develop signs of "major bleeding" as defined by International Society on Thrombosis and Haemostasis (ISTH) criteria (Appendix 3), will have defibrotide held at that time.

#### Per ISTH criteria:

- The term "major bleeding" is defined as symptomatic bleeding in a critical area or organ, including intracranial, intra-spinal, intraocular, retroperitoneal, intra-articular, pericardial, or intramuscular with compartment syndrome.
- Any bleeding associated with a decline in hemoglobin level of ≥ 2.0 g/dl, leading to transfusion of two or more units of whole blood or red cells will constitute a major bleeding episode, and defibrotide will be held.

#### Additional criteria:

- In addition, defibrotide therapy will be held if symptomatic alveolar hemorrhage, macroscopic hematuria, uncontrolled menorrhagia (i.e. requiring therapy), uncontrolled epistaxis (> 10 minutes duration) requiring cauterization and/or nasal packing, or uncontrolled bleeding from a wound site (i.e. bleeding requiring therapeutic intervention) occur.
- Blood tinged endotracheal secretions, microscopic hematuria, mild menorrhagia, and/or epistaxis < 10 minutes duration do not require withholding of drug therapy unless the treating medical team deems that the event requires direct medical intervention.

Therapy may resume once the bleeding diathesis has been resolved for at least 24 hours, and may be restarted at the same dose and dosing schedule. If any further signs of bleeding develop upon re-initiation of therapy, defibrotide would be discontinued and not re-started. Patients who develop signs of CNS hemorrhage or diffuse alveolar hemorrhage

should discontinue study therapy immediately, and will not resume therapy at any time point.

Defibrotide will be held for surgical procedures or to accommodate other urgent intervention (central line placement) without necessitating dose modification. For surgical procedures it is recommended that defibrotide administration be completed > 2 hours prior to the procedure. The DF may be resumed 24 hours after completion of the procedure (or later) based upon the clinical discretion of the treating physician.

In situations in which defibrotide therapy was temporarily held and then resumed, no additional doses of defibrotide will be given to account for any doses that were missed while the drug was being held.

Defibrotide will be discontinued permanently for the development of a "severe or life-threatening (anaphylaxis) hypersensitivity reaction.

Defibrotide will be discontinued permanently if a patient initiates extra-corporeal membrane oxygenation (ECMO) therapy for any reason.

Defibrotide dosing for acute hypersensitivity reactions is discussed in section 6.5 below.

# 6.5 Management of Acute Hypersensitivity Reactions.

If an infusion-related hypersensitivity reaction occurs, the infusion will be emergently held as outlined below. One of the principal investigators, [name] ([name]), [name] ([name]), or [name] ([name]) MUST be contacted immediately (prior to the next dose) so that the study team can determine if further dosing should be held, and/or discontinued altogether. One of the principal investigators will be available 24/7 to discuss potential adverse events or infusion related hypersensitivity reactions that develop in patients receiving study therapy.

Acute Intravenous Infusion Reactions: Emergency equipment and medication for the treatment of infusion reactions must be available for immediate use. All infusion reactions must be reported as AEs (as defined in section 10) and graded using the grading scales as instructed in Section 10.

Interruption of the Intravenous Infusion: The infusion should be interrupted if any of the following AEs are observed:

- Hypotension (blood pressure > 2 standard deviations below baseline)
- Rigors/chills
- Rash, pruritus
- Urticaria (hives, welts, wheals)
- Diaphoresis
- Worsening dyspnea or ventilator status
- Vomiting
- Flushing

The reaction(s) should be treated symptomatically, and the infusion may be restarted at 50% of the original rate, after approval by the study investigators. If study investigators feel there is a medical need for treatment or discontinuation of the infusion other than described above, they should use clinical judgment to provide the appropriate response according to typical clinical practice.

Termination of the Intravenous Infusion: The infusion should be terminated and NOT restarted if any of the following adverse events occur:

- anaphylaxis\*
- laryngeal/pharyngeal edema
- severe bronchospasm
- chest pain
- seizure
- severe hypotension
- other neurological symptoms (confusion, loss of consciousness, paresthesia, paralysis, etc.) any other symptom or sign that, in the opinion of the investigator, warrants termination of the IV infusion

Consider anaphylaxis if the following is observed (Sampson, 2006): acute onset of an illness (minutes to several hours) with involvement of the skin, mucosal tissue, or both (eg, generalized hives, pruritus or flushing, swollen lips-tongue-uvula) AND AT LEAST ONE OF THE FOLLOWING:

- Respiratory compromise (eg, dyspnea, wheeze-bronchospasm, stridor, reduced peak expiratory flow, hypoxemia)
- Reduced blood pressure or associated symptoms of end-organ dysfunction (eg, hypotonia [collapse], syncope, incontinence).

As noted above, one of the principal investigators [[name] ([name]), [name] ([name]), or [name] ([name])] MUST be contacted immediately if any potential hypersensitivity reaction occurs, so that the study team can determine if further dosing should be immediately held, and/or discontinued.

